7.2. Secondary Objectives

- To determine objective response rate (ORR) – depending on availability of follow-up data.
- To describe the demographic and clinical characteristics of patients who have received palbociclib combination treatment in line with locally approved indications.
- To describe dosing and dose changes, interruptions, delays, and discontinuations associated with palbociclib use in clinical practice.
- To describe supportive therapies received by patients while receiving palbociclib combination treatment.
- To summarize adjuvant therapies received for the treatment of early or locally advanced BC (Stages 0-IIIa).
- To describe treatments received in the advanced/metastatic setting, before and after palbociclib combination use.
- To assess QoL of patients receiving palbociclib combination treatment.

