7.3. Exploratory Objectives

- To evaluate time to response (TTR), time to progression (TTP)/PFS associated with palbociclib combination treatment – depending on availability of follow-up data.
- To describe the first immediate subsequent treatment used following end of treatment with palbociclib.

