1. Data is collected in accordance with normal standard of care visits; enter all data available per Data Entry Schedule into the electronic data capture system.
2. For a visit to be considered a follow-up visit, clinical outcomes data must be collected at minimum, in accordance with SOC.
3. Follow-up through End of Study: Enter data at SOC visits post palbociclib treatment.
4. BC treatment: including surgery, radiation, systemic chemotherapy, hormone therapy, and/or targeted therapy, in both neoadjuvant/adjuvant and metastatic disease settings, prior to, during and after palbociclib treatment; supportive care is also collected in the metastatic setting.
5. Data on the first immediate subsequent treatment used after the end of palbociclib treatment should be collected.
6. Clinical outcomes: overall clinical response as judged by treating physician, at intervals per standard of care schedule: progression free survival/time to progression, objective response rate, time to response and overall survival.
7. CBC: Baseline and during palbociclib treatment, enter any CBC during the 1st 3 cycles, then enter Day 1 (or prior to start of a new cycle) CBC for the subsequent cycles as per standard of care.
8. EORTC QLQ-C30 will be collected at baseline (before starting palbociclib) then every 3 months \pm 2 weeks after initiating treatment with palbociclib for the first year of treatment. After the first year of treatment with palbociclib, EORTC QLQ-C30 will be collected every 6 months \pm 4 weeks until the end of treatment with palbociclib.

PFIZER CONFIDENTIAL

CT24-WI-GL02-RF01 3.0 Non-Interventional Study Protocol Template For Primary Data Collection Study

02-Nov-2020

Page 19 of 41

090177e19bc3ff14\Approved\Approved On: 10-Nov-2022 09:28 (GMT)

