4.2. Secondary Endpoints

The secondary endpoints that describe the secondary objectives in the study population and in the subgroups will be:

- Objective response rate (ORR);
- The clinical characteristics (*Time from initial breast cancer diagnosis to recurrence, staging, node status, menopause status, diagnosis for which palbociclib combination was prescribed, sites of metastases, de novo vs. recurrent disease*) of the study population;
- The demographics (*age, ethnicity, weight, family history of BC (BRCA; Testing performed*)) of the study population;
- Palbociclib treatment characteristics (schedule, dose, accompanying treatments, interruption, delays, discontinuation, duration);
- Supportive therapies received during palbociclib combination treatment;
- Adjuvant therapies (name, dose, frequency, initiation time, duration of the adjuvant therapies, and reasons for adjuvant therapy interruption, initiation, and failure) received for the treatment of early/locally advanced BC;
- Treatments received (treatment type, duration, and reasons for treatment changes) in the advanced/metastatic BC setting before and after Palbociclib treatment; Quality of life (QoL) of the patients during Palbociclib treatment.

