4.4. Covariate and Variable Definitions

Patient demographics, clinical characteristics, comorbid conditions and concomitant medications, early/locally advanced and metastatic BC treatment history, current BC treatment, performance status (ECOG), clinical outcomes, laboratory investigations and QoL will be collected. Detailed definitions of the Data Entry Schedule and variables and are provided in Table 1 and Table 3 (Annex 1).

The definitions of clinical outcomes are presented in [Section 6.1](#), [Section 6.2](#), and [Section 6.3](#).

Table 1. Data Entry Schedule

Data collection and entry¹	Baseline	During treatment with Palbociclib	Post treatment with Palbociclib
	SOC Visit 1	SOC Follow-up visits² through End of Treatment with Palbociclib	SOC Follow-up visits through End of Study³
Informed Consent & Inclusion/Exclusion criteria	x		
Patient Demographics, Medical History, Baseline Metastatic Disease Status	x		
BC Diagnosis and Recurrence History	x		
Comorbid Conditions	x	x	
Concomitant Medications	x	x	
BC Treatment⁴	x	x	x⁵
Performance Status (ECOG)	x	x	
Clinical Outcomes⁶	x	x	
Laboratory Investigations, including CBC⁷	x	x	
EORTC QLQ-C30⁸	x	x	

BC=Breast cancer; SOC=Standard of care; CBC=complete blood count; ECOG=Eastern Cooperative Oncology Group; EORTC QLQ-C30=European Organization for the Reasearch and Treatment of Cancer Quality of Life Questionnaire C30.

1. Data is collected in accordance with normal standard of care visits; enter all data available per Data Entry Schedule into the electronic data capture system.
2. For all visits to be considered a follow-up visit, clinical outcomes data must be collected at minimum, in accordance with SOC.
3. Follow-up through End of Study; Enter data at SOC visits post palbociclib treatment.
4. BC treatment: including surgery, radiation, systemic chemotherapy, hormone therapy, and/or targeted therapy, in both neoadjuvant/adjuvant and metastatic disease settings, prior to, during and after palbociclib treatment; supportive care is also collected in the metastatic setting.
5. Data on the first immediate subsequent treatment used after the end of palbociclib treatment should be collected.

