receiving adjuvant therapies	therapies (secondary endpoint)	treatment	Early Breast Cancer Treatment Form	following categories (adjuvant therapy received by patients for treatment of early/locally advanced BC): 
 • Systemic therapy • Adjuvant chemotherapy • Adjuvant hormonal therapy • Experimental adjuvant therapy • Neoadjuvant chemotherapy • Neoadjuvant hormonal therapy • Radiotherapy • Surgery • Other • Unknown
Time between start of palbociclib treatment and end of therapy for early/locally advanced BC (days)	Adjuvant therapies (secondary endpoint)	Prior to Palbociclib treatment	CRF sheet: Early Breast Cancer Treatment Form	Date of initiation of Palbociclib treatment – date of end of therapy for early/locally advanced therapy
Number of patients receiving adjuvant therapies	Adjuvant therapies (secondary endpoint)	Prior to Palbociclib treatment	CRF sheet: Advanced Breast Cancer Treatment Form (prior to palbociclib)	The number of patients in each of the following categories (adjuvant therapy received by patients for treatment of advanced/metastatic BC): 
 • Systemic therapy • MBC chemotherapy • MBC hormonal therapy (other than Palbociclib combination) • Radiotherapy • Surgery • Other • Unknown
Duration of therapy (days)	Adjuvant therapies (secondary endpoint)	Prior to Palbociclib treatment	CRF sheet: Advanced Breast Cancer Treatment Form (prior to palbociclib)	Stop date – start date of therapy
Number of patients receiving adjuvant therapies	Adjuvant therapies (exploratory endpoint)	After Palbociclib treatment	CRF sheet: Subsequent Treatment post-Palbociclib	
 • The number of patients in each of the following categories: • Systemic therapy • Radiotherapy • Surgery • Other • Unknown
Metastatic status	Clinical characteristics (secondary)	At Palbociclib treatment initiation	CRF sheet: Palbociclib Initiation	Metastatic status of advanced BC is categorized as:

PFIZER CONFIDENTIAL

CT24-WI-GL03-RF02 2.0 Non-Interventional Statistical Analysis Plan For Primary Data Collection Study 01-Jun-2020

Variable	Role	Time point(s)	Data source(s)	Operational definition
	endpoint), stratification variable		Medical History, Palbociclib Baseline Tumor Assessment	
 De-novo metastatic BC Recurrent/relapse advanced BC

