Table Shell 38 - Descriptive summary table of therapies of the advanced/metastatic BC patients (stages IIIb-IV) before Palbociclib treatment.

Variable	Summary statistic
Number of patients who received adjuvant therapies before Palbociclib treatment	XX
Systemic therapy	XX (xx%)
-MBC chemotherapy	XX (xx%)
-MBC hormonal therapy (other than Palbociclib combination)	XX (xx%)
Radiotherapy	XX (xx%)
Surgery	XX (xx%)
Other	XX (xx%)
Unknown	XX (xx%)
Missing	XX (xx%)
Duration of therapy (days)	
Mean (SD)	xx.x (xx.x)
Q1, median, Q3	xx.x, xx.x, xx.x
Min, max	xx.x, xx.x
Missing	XX (xx%)

090177a099673e39a54dc25f1a9a15reed On: 28-Mar-2023 09:56 (GMT)

090177a099673e39a54dc25f1a9a15reed On: 28-Mar-2023 09:56 (GMT)

Table Shell 40 - Descriptive summary table of therapies of the advanced/metastatic BC patients (stages IIb-IV) by line of endocrine therapy *before* Palbociclib treatment.

Variable	Line of endocrine therapy	
	1 st	2 nd
Number of patients who received adjuvant therapies before Palbociclib treatment	XX	XX
Systemic therapy	XX (xx%)	XX (xx%)
-MBC chemotherapy	XX (xx%)	XX (xx%)
-MBC hormonal therapy (other than Palbociclib combination)	XX (xx%)	XX (xx%)
Radiotherapy	XX (xx%)	XX (xx%)
Surgery	XX (xx%)	XX (xx%)
Other	XX (xx%)	XX (xx%)
Unknown	XX (xx%)	XX (xx%)
Missing	XX (xx%)	XX (xx%)
Duration of therapy (days)		
Mean (SD)	xx.x (xx.x)	xx.x (xx.x)
Q1, median, Q3	xx.x, xx.x, xx.x	xx.x, xx.x, xx.x
Min, max	xx.x, xx.x	xx.x, xx.x
Missing	XX (xx%)	XX (xx%)

Table Shell 41 - Descriptive summary table of therapies of the advanced/metastatic BC patients (stages IIb-IV) by country *before* Palbociclib treatment.

Variable	Country						
	Egypt	Jordan	Lebanon	KSA	Qatar	Morocco	UAE
Number of patients who received adjuvant therapies before Palbociclib treatment	XX	XX	XX	XX	XX	XX	XX
Systemic therapy	XX (xx%)	XX (xx%)	XX (xx%)	XX (xx%)	XX (xx%)	XX (xx%)	XX (xx%)
-MBC chemotherapy	XX (xx%)	XX (xx%)	XX (xx%)	XX (xx%)	XX (xx%)	XX (xx%)	XX (xx%)
-MBC hormonal therapy (other than Palbociclib combination)	XX (xx%)	XX (xx%)	XX (xx%)	XX (xx%)	XX (xx%)	XX (xx%)	XX (xx%)
Radiotherapy	XX (xx%)	XX (xx%)	XX (xx%)	XX (xx%)	XX (xx%)	XX (xx%)	XX (xx%)
Surgery	XX (xx%)	XX (xx%)	XX (xx%)	XX (xx%)	XX (xx%)	XX (xx%)	XX (xx%)
Other	XX (xx%)	XX (xx%)	XX (xx%)	XX (xx%)	XX (xx%)	XX (xx%)	XX (xx%)
Unknown	XX (xx%)	XX (xx%)	XX (xx%)	XX (xx%)	XX (xx%)	XX (xx%)	XX (xx%)
Missing	XX (xx%)	XX (xx%)	XX (xx%)	XX (xx%)	XX (xx%)	XX (xx%)	XX (xx%)
Duration of therapy (days)							

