Q1 (95% CI)	xx.x (xx.x)	xx.x (xx.x)	xx.x (xx.x)
Median (95% CI)	xx.x (xx.x)	xx.x (xx.x)	xx.x (xx.x)
Q3 (95% CI)	xx.x (xx.x)	xx.x (xx.x)	xx.x (xx.x)
Min, max	XX.x, xx.,x	XX.x, xx.,x	XX.x, xx.,x
Missing	XX (xx%)	XX (xx%)	XX (xx%)
Progression free survival (PFS)			
N at risk at the beginning	XX	XX	XX
N with event (disease progression)	XX (xx%)	XX (xx%)	XX (xx%)
N censored	XX (xx%)	XX (xx%)	XX (xx%)
Q1 (95% CI)	xx.x (xx.x)	xx.x (xx.x)	xx.x (xx.x)
Median (95% CI)	xx.x (xx.x)	xx.x (xx.x)	xx.x (xx.x)
Q3 (95% CI)	xx.x (xx.x)	xx.x (xx.x)	xx.x (xx.x)
Min, max	XX.x, xx.,x	XX.x, xx.,x	XX.x, xx.,x
Missing	XX (xx%)	XX (xx%)	XX (xx%)

Figure Shell 1 - Kaplan Meier plot to describe time to response by type of combination therapy.

Figure 2. Kaplan Meier plot to describe time to response by type of combination therapy.

The same format will be used to:

Figure Shell 2 - Kaplan Meier plot to describe time to progression by type of combination therapy.

090177e1990673e39a54dc25f1a9a15read On: 28-Feb-2023 09:56 (GMT)

090177e1990673e39a54dc25f1a9a15read On: 28-Feb-2023 09:56 (GMT)

090177e1990673e39a54dc25f1a9a15read On: 28-Feb-2023 09:56 (GMT)

090177e1990673e39a54dc25f1a9a15read On: 28-Feb-2023 09:56 (GMT)

Table Shell 64 - Descriptive summary table of the first immediate subsequent treatment used following end of treatment with Palbociclib by line of treatment.

Variable	Line of endocrine therapy	
	1 st	2 nd
Number of patients who received adjuvant therapies after Palbociclib treatment	XX	XX
Systemic therapy	XX (xx%)	XX (xx%)
Radiotherapy	XX (xx%)	XX (xx%)
Surgery	XX (xx%)	XX (xx%)
Other	XX (xx%)	XX (xx%)
Unknown	XX (xx%)	XX (xx%)
Missing	XX (xx%)	XX (xx%)

Table Shell 65 - Descriptive summary table of the first immediate subsequent treatment used following end of treatment with Palbociclib by country.

Variable	Country						
	Egypt	Jordan	Lebanon	KSA	Qatar	Morocco	UAE
Number of patients who received adjuvant therapies after Palbociclib treatment	XX	XX	XX	XX	XX	XX	XX
Systemic therapy	XX (xx%)	XX (xx%)	XX (xx%)	XX (xx%)	XX (xx%)	XX (xx%)	XX (xx%)
Radiotherapy	XX (xx%)	XX (xx%)	XX (xx%)	XX (xx%)	XX (xx%)	XX (xx%)	XX (xx%)
Surgery	XX (xx%)	XX (xx%)	XX (xx%)	XX (xx%)	XX (xx%)	XX (xx%)	XX (xx%)
Other	XX (xx%)	XX (xx%)	XX (xx%)	XX (xx%)	XX (xx%)	XX (xx%)	XX (xx%)
Unknown	XX (xx%)	XX (xx%)	XX (xx%)	XX (xx%)	XX (xx%)	XX (xx%)	XX (xx%)
Missing	XX (xx%)	XX (xx%)	XX (xx%)	XX (xx%)	XX (xx%)	XX (xx%)	XX (xx%)

090177a099673e39a54dc25f1famp15reed On: 28-Mar-2023 09:56 (GMT)

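### The post-palbociclib treatment tables keep systemic therapy as one undivided row, so they describe the next treatment only by modality and cannot be set against the pre-palbociclib tables

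*SAP*

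**What the plan says.** Two protocol objectives depend on treatment after palbociclib. The secondary one (Protocol 7.2) is "To describe treatments received in the advanced/metastatic setting, before and after palbociclib combination use". The exploratory one (Protocol 7.3) is "To describe the first immediate subsequent treatment used following end of treatment with palbociclib".

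SAP 4.2 defines the secondary endpoint as "Treatments received (treatment type, duration, and reasons for treatment changes) in the advanced/metastatic BC setting before and after Palbociclib treatment". SAP 6.2 assigns the after part of that objective to Table Shell 62, and SAP 6.3 assigns the exploratory objective to the same shell. Both are stratified in Shells 63–69.

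For data collection, footnote 4 of the data entry schedule (Protocol Table 2, SAP Table 1) reads in the SAP: "BC treatment: including surgery, radiation, systemic chemotherapy, hormone therapy, and/or targeted therapy, in both neoadjuvant/adjuvant and metastatic disease settings, prior to, during and after palbociclib". Footnote 5 adds that the first treatment following palbociclib should be recorded.

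For reporting, Annex 1 sources the variable from "CRF sheet: Subsequent Treatment post-Palbociclib" and gives it five classes: systemic therapy, radiotherapy, surgery, other and unknown. Shells 64, 65, 68 and 69 carry those classes plus Missing, under the header "Number of patients who received adjuvant therapies after Palbociclib treatment".

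**The concern.** The reporting categories are coarser than the endpoint, than the data to be collected, and than the tables for treatment before palbociclib. Chemotherapy, hormone therapy and targeted therapy are all systemic, so all three go into one row. A treatment-pattern study in HR+/HER2- advanced disease will be read for exactly that distinction, and the shells as written remove it.

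The second cost is comparability. The secondary objective pairs treatment before with treatment after palbociclib, but only the before tables carry a class split and a duration.

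**Working it through.** There is no design figure to reproduce, so the check sets the passages side by side.

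| Place | Split of systemic therapy | Duration | Reason for change |
|---|---|---|---|
| SAP 4.2 endpoint, before and after | Type promised | Promised | Promised |
| Data entry schedule, footnote 4, all periods | Chemotherapy, hormone, targeted | Not stated | Not stated |
| Shell 30, early disease | Adjuvant and neoadjuvant chemotherapy and hormonal therapy, experimental adjuvant | No; time from end of therapy to palbociclib | No |
| Shell 38, advanced disease before palbociclib | Chemotherapy, hormonal | Yes | No |
| Annex 1, after palbociclib | None | No | No |
| Shells 64, 65, 68, 69, after palbociclib | None | No | No |

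**The split is available elsewhere in the SAP.** In Shell 38, systemic therapy has a chemotherapy sub-row and one beginning "MBC hormonal therapy (other than Palbociclib combination". Shells 40–45 follow the same pattern. None has a targeted-therapy row, although footnote 4 lists targeted therapy as collected before palbociclib too.

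**No other listed table fills the gap.** Shell 14 gives reasons for stopping palbociclib and a yes/no for another treatment afterwards. It does not say what that treatment was, and it is not cross-tabulated with it.

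**What the row cannot distinguish.** Assume 100 patients start a next treatment, 80 of them systemic, each counted in one systemic class.

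- Cohort A: 70 chemotherapy + 10 hormone or targeted = 80, printed as 80/100 = 80%.
- Cohort B: 10 chemotherapy + 70 hormone or targeted = 80, printed as 80/100 = 80%.

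The two cohorts print identically. The assumed totals do not matter, because any two mixes with the same systemic total give the same row.

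**How many patients might be involved (illustration only).** Inputs are N = 200 (Protocol 8.1) and the extremes of the palbociclib-arm PFS medians cited for the phase III trials in Protocol 6.1, 24.8 and 9.5 months. Assume exponential PFS and that each patient who progresses within 24 months starts a next treatment.

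- Number progressing = 200 × (1 − 0.5^(24/median)).
- Median 24.8 months: 200 × 0.489 ≈ 98.
- Median 9.5 months: 200 × 0.826 ≈ 165.

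The documents give no systemic share. At an assumed 70% to 99%, the single row would hold about 68–97 of 98, or 116–164 of 165.

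**Where the loss would show.** Protocol 6.1 describes endocrine therapy as the main treatment in this disease and chemotherapy for heavy visceral burden or rapid progression. Shell 68 stratifies the next treatment by visceral versus non-visceral site, yet it has no row in which a chemotherapy difference could appear.

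**The case against.** Several points on the other side have force.

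- **The main table cannot be seen.** The bodies of Shells 62, 63, 66 and 67 are not readable in the text available, so the overall table is inferred. This stands as a caveat. The Annex 1 definition and four matching stratified shells make a finer Shell 62 unlikely, but do not exclude it. SAP 6.2 also speaks of describing the most common therapies, which leaves some room.
- **The objectives are only to describe.** A modality table is a description, SAP 4.2 does not define treatment type, and Shell 14 covers part of the reasons for change. This stands against any claim that the objectives go unanswered: they are answered coarsely. It does not explain why the same SAP uses a finer class before palbociclib.
- **The distribution is unknown.** A reader might infer that nearly every patient falls in the systemic row, or that the stratified tables would show near-identical percentages. The documents do not support either. They report no distribution of next treatments, the background describes usual treatment in this disease rather than treatment after palbociclib, and nothing says the rows are mutually exclusive.
- **The CRF is not supplied.** Footnotes 4 and 5 together support class-level collection after palbociclib. Recording of individual agents is not shown.
- **The impact is bounded.** The study is descriptive, and no primary endpoint, sample size or test is touched.

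**Conclusion.** The concern holds as one of insufficient granularity. Annex 1 and the readable shells report treatment after palbociclib by modality only, with no duration or reason for change, although SAP 4.2 promises type, duration and reasons. Followed exactly, they cannot separate a move to chemotherapy from a move to hormone or targeted therapy, and the before and after halves of the secondary objective cannot be compared by class.

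The conclusion rests on the Annex 1 definition and the four readable shells, and assumes that the unreadable shells follow them. It needs no assumption about how many patients receive systemic therapy; the counts above only illustrate scale. Saying that the objectives fail altogether would go too far, since modality is reported and the treatments before palbociclib are described by class. The change is worth making before the tables are programmed, but it bears on secondary and exploratory description only.

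**What to change.** 1. In Annex 1 (the row for treatment after palbociclib) and Shells 62–69, split systemic therapy into the classes footnote 4 already names: chemotherapy, hormone therapy and targeted therapy. Flag combinations, and list the most common agents if the CRF records drug names.
2. Add duration and reason for change where these are collected, marking treatments still ongoing at the end of follow-up. Otherwise narrow the SAP 4.2 endpoint to what will be reported.
3. Add a targeted-therapy row to Shells 38–45 so that both halves of the objective use the same classes.
4. Relabel the header of Shells 62–69, and the matching Annex 1 entry, as first subsequent treatment instead of adjuvant therapy.

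The cost is wording in Annex 1 and the shells plus some coding of treatment records. No new data collection is needed provided the CRF holds treatment class after palbociclib, as footnotes 4 and 5 indicate; check the CRF before committing to agent-level rows or durations.
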